4.4. Study design summary

A summary of the sample size, sampling approach, and research design for the three sub-studies is outlined in Table 2.

Table 2. Summary of sampling size, sampling approach and research design

Study	Total Sample	Sampling Approach	Design	Primary Outcome Measure
-------	--------------	-------------------	--------	-------------------------

1	120	Stratified: 60 MCI and 60 SCD, matched to population demographics	Prospective between group quasi-experimental research design	CoCoA-PAD index and subtest scores.
2	81	Convenience: based on proximity to Plymouth	Cross sectional research design	CoCoA-PAD subtest scores Diffusion tensor imaging measures (FA, RD and MD) of key white matter tracts Neurite Density Index (NDI) of key grey matter regions of interest.
3	36	Stratified: 18 people with prodromal AD and 18 healthy controls.	Retrospective between group quasi-experimental research design	Change scores on CoCoA-PAD subtests (time 2 – time 1 subtest scores).

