11.4. Provisional Data Analysis

The CI will work with a medical statistician, [name], to finalise the data analysis plan, and will publish this on Open Science Framework, prior to the start of data collection. This will ensure both rigour and transparency. A provisional data analysis plan is outlined for each sub-study below. Furthermore, Appendix 2 provides a specific breakdown of the hypotheses and analysis plan for each CoCoA-PAD subtest. This should be considered provisional and may be subject to change prior to the start of the study.

Study 1: Diagnostic Accuracy of CoCoA-PAD Subtests

The aim of this study is to test whether each CoCoA-PAD subtest can distinguish between healthy controls and people with preclinical and prodromal Alzheimer’s disease. This study will use a Welch’s ANOVA to accommodate unequal variances and sample sizes ($k=3$, healthy controls, preclinical AD, and prodromal AD) and Games–Howell post hoc test. A series of receiver operator curves, area under the curves, and optimised sensitivity and specificity values based on Youden index, will be calculated to measure the diagnostic accuracy of each subtest also.

Study 2: The relationship between CoCoA-PAD subtests and the health of key brain regions

Associations between CoCoA-PAD subtest scores and regional brain volume, density and connectivity will first be explored using Spearman correlations, adjusted for false discovery rate using the Benjamini-Hochberg Procedure. Multiple linear regression models will then be used to assess the predictive value of MRI-derived volumetric measures on CoCoA-PAD performance, adjusting for potential confounders including age, sex, education, and intracranial volume. Model fit and assumptions will be evaluated to ensure robustness.

Study 3: Testing whether CoCoA-PAD is sensitive to pathological cognitive decline in AD

Change scores on CoCoA-PAD subtests will be calculated by subtracting time 1 score from time 2 score. As such, negative change scores will denote a decline in performance. A series of *t* tests will be used to test whether the prodromal AD group exhibit higher levels of cognitive decline over a one-year interval. To control for the false discovery rate (FDR) across multiple *t*-tests, the Benjamini–Hochberg procedure was applied with a threshold of $q = 0.05$. This method adjusts *p*-values to reduce the risk of Type I error when conducting multiple comparisons.

Data Analysis Software

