Fractional Anisotropy (FA), Mean Diffusivity (MD), Radial Diffusivity (RD), Axial Diffusivity (AD) in a priori tracts (fornix, parahippocampal cingulum, uncinate fasciculus, inferior longitudinal fasciculus, inferior fronto-occipital fasciculus, arcuate fasciculus, superior longitudinal fasciculus, vertical occipital fasciculus, corpus callosum, optic radiations, frontostriatal pathways)

NODDI

Neurite Density Index (NDI), Orientation Dispersion Index (ODI), Free Water Fraction (FWF) in cortical ROIs: entorhinal cortex, hippocampus, perirhinal cortex, fusiform gyrus, posterior parietal cortex, precuneus, occipital cortex, anterior cingulate cortex, dorsolateral prefrontal cortex, primary auditory cortex, frontal and parietal eye fields.

T1-weighted volumetry/thickness

Grey matter volume, cortical thickness in medial temporal lobe (hippocampus, entorhinal cortex), fusiform gyrus, posterior parietal lobe, precuneus, occipital cortex, anterior cingulate cortex, dorsolateral prefrontal cortex, anterior temporal lobe

SUBTEST-LEVEL ANALYSIS PLAN

PREMORBID COGNITIVE ABILITY

Paragraph Reading Test

- Cognitive Theory: Index of premorbid verbal ability; not sensitive to AD pathology.
- Diagnostic Hypothesis: No diagnostic role.
- Neuroimaging Hypotheses: None (excluded from MRI analysis).

MEMORY

SILT (Semantic Interference during Learning Test)

- Cognitive Theory: Tests susceptibility to semantic interference; hippocampal–entorhinal associative binding.
- Diagnostic Hypothesis: Distinguishes preclinical vs healthy, and prodromal vs healthy.
- Neuroimaging Hypotheses:
 - DTI tracts: fornix; parahippocampal cingulum; uncinate fasciculus; superior longitudinal fasciculus.
 - NODDI regions: entorhinal cortex; hippocampus (CA1, subiculum); dorsolateral prefrontal cortex; anterior cingulate cortex.
 - T1 (secondary): hippocampal & entorhinal thickness.

MANE (Matching Animals and Name Examination)

- Cognitive Theory: Tests associative binding of names to animal images; anterior temporal & fusiform integration.
- Diagnostic Hypothesis: Distinguishes preclinical vs healthy, and prodromal vs healthy.
- Neuroimaging Hypotheses:
 - DTI tracts: inferior longitudinal fasciculus; inferior fronto-occipital fasciculus; uncinate fasciculus; arcuate fasciculus.
 - NODDI regions: entorhinal cortex; fusiform gyri; anterior temporal cortex; perirhinal cortex.
 - T1 (secondary): anterior temporal volume; fusiform thickness.

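### Study 2 specifies confounder-adjusted regression only for the volumetric MRI measures; the primary DTI and NDI measures are given only unadjusted Spearman correlations

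*Protocol*

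**What the plan says.** Protocol section 11.4, Study 2, sets out two steps.

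- **Step 1** covers all three families of brain measure: "regional brain volume, density and connectivity will first be explored using Spearman correlations". The only adjustment attached to it is for multiplicity: "adjusted for false discovery rate using the Benjamini-Hochberg Procedure".
- **Step 2** is narrower: "Multiple linear regression models will then be used to assess the predictive value of MRI-derived volumetric measures on CoCoA-PAD performance". Only these models carry covariates, namely age, sex, education and intracranial volume.

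The ranking of the measures is given elsewhere in the protocol.

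- Table 2 (section 4.4) lists the Study 2 primary outcomes as the CoCoA-PAD subtest scores and "Diffusion tensor imaging measures (FA, RD and MD) of key white matter tracts Neurite Density Index (NDI) of key grey matter regions of interest". It lists no volumetric measure.
- The summary table in Appendix 2 heads both the DTI tract column and the NODDI region column as primary. The subtest entries mark T1 as secondary, for example "T1 (secondary): hippocampal & entorhinal thickness" under SILT.
- Section 11.3 bases the Study 2 sample size on a single coefficient in a multiple linear regression (f² = 0.1, alpha 0.05, power 0.8, minimum 64).

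**The concern.** The covariate-adjusted model and the primary measures do not meet. The measures ranked secondary get the adjusted regression; those ranked primary get a correlation with no covariates.

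The protocol itself treats age, sex and education as possible confounders. It recruits from age 65 with no stated upper limit, deliberately spreads educational attainment from no qualification to Level 4 (Table 1), and draws Study 2 from every diagnostic group. In such a sample both test scores and white-matter or neurite measures may vary with age and education. Primary objective iii is to relate subtests to neurodegeneration. A tract-by-tract pattern that mostly tracked age could be reported as specific neural associations of individual subtests.

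**Working it through.** **1. The plan's own figure.** For one coefficient in a fixed-model regression, the noncentrality is √(f²·N) with N − k − 1 degrees of freedom. With f² = 0.1 and k = 5 (one MRI measure plus the four named covariates):

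| Alpha 0.05 | N for power 0.80 | Power at 64 | Power at 81 |
|---|---|---|---|
| One-sided | 64 | 0.80 | 0.88 |
| Two-sided | 81 | 0.70 | 0.80 |

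The stated 64 reproduces exactly, but only one-sided; section 11.3 does not state the sidedness. The planned 81 carries the adjusted model at power 0.80 two-sided, per measure, before multiplicity correction and with no lost scans.

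**2. Measures against models (Study 2).**

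| Measure | Rank | Unadjusted Spearman | Adjusted regression |
|---|---|---|---|
| DTI FA, RD, MD | Primary (Table 2, Appendix 2) | Yes | Not specified |
| NODDI NDI | Primary (Table 2, Appendix 2) | Yes | Not specified |
| NODDI ODI, FWF | Not in Table 2; under NODDI regions headed primary in Appendix 2 | Yes | Not specified |
| T1 volumes | Absent from Table 2; secondary in Appendix 2 subtest entries | Yes | Yes |

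**3. Size of the risk, under an assumption.** Suppose age correlates r with both a subtest and a brain measure, and nothing else links them. The induced correlation is r × r. The test uses Fisher's z with the Spearman variance factor 1.06 at N = 81, so SE = √(1.06/78) = 0.117. The shift is atanh(r²)/SE, and rejection is two-sided at a nominal 5%.

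| Age correlation r | Induced r² | Shift | Rejection (formula) | Rejection (simulation, 10,000 runs) | Age-partial Spearman (simulation) |
|---|---|---|---|---|---|
| 0.2 | 0.04 | 0.34 | 6% | 6% | 5% |
| 0.3 | 0.09 | 0.77 | 12% | 12% | 5% |
| 0.4 | 0.16 | 1.38 | 28% | 27% | 6% |
| 0.5 | 0.25 | 2.19 | 59% | 58% | 5% |

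**4. Does Benjamini-Hochberg cure it?** The Appendix 2 summary table gives 42 subtest–tract pairs and 51 subtest–region pairs, so the Table 2 primary metrics make 42 × 3 + 51 = 177 tests. These were simulated as one family at q = 0.05, with age the only link and measures independent given age. Unadjusted Spearman plus Benjamini-Hochberg declared at least one association in 34%, 87% and 100% of studies at r = 0.3, 0.4 and 0.5, with on average 0.6, 11 and 76 declarations. Partial Spearman plus Benjamini-Hochberg stayed at 5–6%. The procedure controls chance findings; a correlation induced by a shared cause is not a chance finding.

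**The case against.** **The plan is provisional.** Section 11.4 says so, and section 4.6 promises a statistician-approved, pre-registered plan. Covariate detail may properly be left to that plan. But the protocol is not silent here: it assigns a model to one family of measures and not to the others, against its own ranking.

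**Volumetric may be loose drafting for all MRI measures.** The regression-based power calculation supports this, and Spearman is described only as a first exploratory step. It may well be what was intended. As written, though, one sentence separates volume from density and connectivity and the next names volume alone. If regression was meant for all, the text still has to say so.

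**Objective iii asks only for a relationship.** It claims no effect independent of age. That is fair as to wording, but the plan itself adjusts for age when it examines volumes, so the same standard should reach the primary measures.

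**Stronger readings to avoid.** A reader might infer that:
- false discovery rate control is confined to the unadjusted step. Section 4.6 promises it for the analysis plan generally; section 11.4 merely does not repeat it after the Study 2 regressions.
- all NODDI metrics are primary outcomes. Table 2 names only NDI; the wider claim rests on an Appendix 2 column heading.
- volumetry is ranked secondary everywhere. Section 4.2 lists it first without a rank, and the general T1 list in Appendix 2 carries none.
- the results will be confounded by age. The documents give no age correlations, and at 0.2 the per-test error is close to nominal.

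**Conclusion.** The mismatch stands on the text. No section gives the primary DTI and NDI measures a covariate-adjusted model, while the lower-ranked volumetric measures have one. Confounding by age or education is a plausible risk, not something the documents demonstrate. Its size rests on assumed, equal age correlations with both measures and no other link: about 6% to 59% rejection per nominal 5% test for correlations of 0.2 to 0.5. Those are per-test rates before false discovery rate correction, not the plan's final decision error. Design and planned sample size are unaffected.

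**What to change.** In section 11.4, Study 2:

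1. Extend the adjusted model to the primary DTI (FA, RD, MD) and NDI measures and to the other NODDI measures, as linear regression or partial Spearman with age, sex and education. Use intracranial volume for volumes only.
2. State that the inference for objective iii rests on this adjusted model.
3. Apply the Benjamini-Hochberg correction promised in section 4.6 to the adjusted p-values.
4. Report the unadjusted Spearman correlations as descriptive.
5. While editing, state the sidedness behind the minimum of 64 in section 11.3.

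The cost is plan wording, best settled before registration on the Open Science Framework, and about 3 degrees of freedom per model with education as one term (years of education are recorded, section 9.3). Age, gender and education are already collected (section 6.2); the text should say that recorded gender serves as the sex covariate, if that is intended.

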4.2. Study 2. Relationship Between Brain Health and CoCoA-PAD Performance

Participants

All participants from Study 1 who live within driving distance of Plymouth ($n=81$) will be invited to undergo a magnetic resonance imaging (MRI) assessment. As such, study 2 will consist of participants who fit into each diagnostic criteria from Study 1.

Sampling

This study will use a convenience sampling procedure based on recruitment to Study 1 and participant location. A cross-sectional design will be employed.

Procedure

Participants will undergo MRI assessment following their participation in Study 1.

Measures

This study will measure the relationship between CoCoA-PAD subtest scores and key indicators of neuronal health. MRI data will be obtained using both single (T1-weighted) and multi-shell imaging approaches.

The specific measures of brain health include:

1. Volumetric measures using T1-weighted imaging of key regions of interest (ROI) associated with early Alzheimer's disease.
2. Diffusion Tensor Imaging (DTI) measures, including Fractional Anisotropy (FA), Radial Diffusivity (RD) and Mean Diffusivity (MD) of defined white matter tracts associated with Alzheimer's disease.
3. Neurite Density Index (NDI), Free Water Fraction (FWF), and Orientation Dispersion Index (ODI) metrics from Neurite Orientation Dispersion and Density Imaging (NODDI) of key grey matter regions of interest.

Figure 3 illustrates the estimated post-diagnostic participant numbers from Study 1.

4.3. Study 3. Measuring the Ability of CoCoA-PAD Subtests at Determining Change Over Time

Participants

A sub-sample of 36 participants from the Study 1 sample will be reassessed on CoCoA-PAD approximately one year after their initial engagement in the CoCoA-PAD study. 18 participants will be selected from both the healthy control and prodromal AD groups.

Sampling

This study will use a criterion based sampling procedure, selecting participants from Study 1 retrospectively based on diagnostic classification.

Procedure

Participants will complete the CoCoA-PAD battery a second time, approximately 11-15 months after their initial assessment.

Measures

The primary outcome measure will be change in scores on CoCoA-PAD subtests (time 2 – time 1 score). This study will therefore use a retrospective (known-group) between-group quasi-experimental research design.

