11.3. Sample Size

Given that there are three independent studies, a justification of the proposed sample is outlined for each study.

Study 1: Diagnostic Accuracy of CoCoA-PAD Subtests

The aim of this study is to test whether CoCoA-PAD subtests can distinguish between healthy controls (i.e., people with subjective memory problems without any evidence of AD biomarkers or cognitive decline) and people with preclinical and prodromal Alzheimer's disease. This study uses a prospective research design, and therefore exact participant numbers in each diagnostic criteria cannot be determined until after data collection. Figure 3 provides an estimate of the final sample composition, which includes of 36 healthy controls, 18 people with preclinical AD, and 40 people with prodromal AD. A power calculation using a fixed one-way ANOVA (estimated effect size $f = 0.33$ (moderate effect), $k = 3$) required a minimum sample of 90 to achieve the required power ($\alpha = 0.05$, $1-\beta = 0.8$). Based on current projections (36 controls, 18 preclinical AD, and 40 with prodromal AD), this would be achieved.

Study 2: The relationship between CoCoA-PAD subtests and the health of key brain regions

This study aimed to measure the strength of the association between key brain regions and performance on CoCoA-PAD subtests. It includes a subgroup of study 1 participants. A power calculation using a linear multiple regression (fixed model, single regression coefficient, effect size f^2 (0.1, small) required a minimum sample of 64 participants to achieve the required power ($\alpha = 0.05$, $1-\beta = 0.8$).

Study 3: Testing whether CoCoA-PAD is sensitive to pathological cognitive decline in AD

This study aimed to compare 1 year change score (time 2 score – time 1 score) on CoCoA-PAD subtest scores in people with early Alzheimer’s disease and healthy controls. It includes a subgroup of study 1 participants. A power calculation using a matched pairs *t* test (Cohen’s *d* = 0.5 (moderate)) required a sample of 27 to achieve the required power ($\alpha = 0.05$, $1-\beta = 0.8$).

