- Cognitive Theory: Tests inhibitory control, attentional regulation, and eye-movement control.
- Diagnostic Hypothesis: Distinguishes prodromal vs healthy.
- Neuroimaging Hypotheses:
 - DTI tracts: superior longitudinal fasciculus; frontostriatal tracts; cingulum bundle.

- NODDI regions: entorhinal cortex; dorsolateral prefrontal cortex; anterior cingulate cortex; frontal eye fields; parietal eye fields.
 - T1 (secondary): frontal cortical thickness.
-

PERFORMANCE VALIDITY

CoCoA-PAD PVT

- **Cognitive Theory:** Ensures task engagement and response validity.
- **Diagnostic Hypothesis:** Not diagnostic.
- **Neuroimaging Hypotheses:** None.

	Cognitive theory (summary)	Diagnostic hypothesis	Key DTI tracts (primary)	Key NODDI regions (primary)
Paragraph Reading (premorbid)	Premorbid ability	No diagnostic role	–	–
SILT	Semantic interference; associative binding	Preclinical vs HC; Prodromal vs HC	Fornix; Parahippocampal cingulum; Uncinate; SLF	Entorhinal; Hippocampus; DLPFC; ACC
MANE	Associative binding (names ↔ animals)	Preclinical vs HC; Prodromal vs HC	ILF; IFOF; Uncinate; Arcuate	Entorhinal; Fusiform; Perirhinal; Anterior temporal
COBALT	Conjunctive binding of colour/object/location; spatial prediction	Preclinical vs HC; Prodromal vs HC	SLF; VOF; ILF; Uncinate	Entorhinal; Posterior parietal; Precuneus; Perirhinal; Occipital
ALF	Accelerated forgetting (consolidation deficit)	Prodromal vs HC	Fornix; Parahippocampal cingulum; Uncinate	Entorhinal; Hippocampus; Anterior temporal
TASP	Allocentric spatial representation	Preclinical vs HC; Prodromal vs HC	Fornix; Posterior cingulum; SLF	Entorhinal; Hippocampus; Precuneus; Retrosplenial; Parietal
Clock Drawing	Visuoconstruction & executive control	Prodromal vs HC	SLF; IFOF	Entorhinal; Posterior parietal; DLPFC
Motion Perception	Dorsal-stream visuospatial binding	Preclinical vs HC	Optic radiations; VOF; SLF	Entorhinal; MT/V5; Parietal; Precuneus
Odd-One-Out	Object discrimination (perirhinal)	Prodromal vs HC	ILF; Uncinate; IFOF	Entorhinal; Perirhinal; Fusiform; Occipital
Overlapping Objects	Conjunctive perceptual binding	Prodromal vs HC	ILF; Uncinate; IFOF	Entorhinal; Perirhinal; Fusiform
Verbal Fluency	Semantic retrieval & executive	Prodromal vs HC	Arcuate; UF; IFOF; FAT	Entorhinal; Anterior temporal; LIFG; ACC
Connected Speech	Discourse/semantic integration	Exploratory	Arcuate; IFOF; UF	Entorhinal; Anterior temporal; Perisylvian

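### In Study 2 the covariate-adjusted regressions are specified only for T1 volumes, ranked secondary; the primary DTI and NODDI measures get unadjusted Spearman correlations and are open to confounding by age, sex and education

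*Protocol*

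**What the plan says.** **Ranking.** Table 2 (section 4.4) gives the Study 2 primary outcomes as CoCoA-PAD subtest scores, "Diffusion tensor imaging measures (FA, RD and MD) of key white matter tracts", and the Neurite Density Index (NDI) in key grey matter regions. T1 volumes are not in that cell. The summary table of Appendix 2 heads one column "Key DTI tracts (primary") and marks the NODDI column the same way. The subtest entries put T1 measures one rank lower, for example "T1 (secondary): hippocampal & entorhinal thickness" under SILT, and do so for every subtest with imaging hypotheses.

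**Analysis.** Section 11.4 takes volume, density and connectivity together in a first, exploratory step: Spearman correlations with Benjamini-Hochberg control and no covariates. The second step reads "Multiple linear regression models will then be used to assess the predictive value of MRI-derived volumetric measures on CoCoA-PAD performance", with age, sex, education and intracranial volume as potential confounders. Nowhere else does the protocol adjust a DTI or NODDI measure for a covariate.

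**Sample size.** Section 11.3 rests on regression: "A power calculation using a linear multiple regression (fixed model, single regression coefficient", with an f² of "0.1, small) required a minimum sample of 64 participants". Section 4.2 takes its sample from Study 1 participants "who live within driving distance of Plymouth ($n=81$) will be invited".

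**The concern.** The strength of the analysis runs opposite to the ranking of the measures. Secondary measures get a model that adjusts for age, sex and education; primary measures get a correlation that does not.

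Eligibility starts at age 65 with no upper limit in Table 3, and Table 1 deliberately spreads education from no qualification to Level 4. These covariates will therefore vary in the sample. If age, say, is related both to a diffusion measure and to a subtest score, the two will correlate even when neither says anything about the other at a given age. Benjamini-Hochberg does not address this. It controls false rejections of the hypothesis of zero marginal correlation, and under confounding that correlation is truly non-zero.

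At stake is the primary-ranked part of objective iii. A diffusion finding obtained as written could not be told apart from ordinary ageing. Adding adjusted diffusion models after the results are known would be post hoc against a pre-registered plan.

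**Working it through.** **1. The plan's own figure.** Inputs from 11.3: f² = 0.1, alpha 0.05 (sidedness not stated), power 0.80, one coefficient. With p predictors, the test of one coefficient has noncentrality √(f²·N) and N − p − 1 degrees of freedom. Take p = 5 (MRI measure, age, sex, education, intracranial volume):

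| N | Noncentrality | df | Power, one-sided | Power, two-sided |
|---|---|---|---|---|
| 64 | √6.4 = 2.53 | 58 | 0.80 | 0.70 |
| 81 | √8.1 = 2.85 | 75 | 0.88 | 0.80 |

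The stated 64 is reproduced as a one-sided test. A two-sided test needs 81, the number invited. Neither figure changes for any p tried between 1 and 8, so extending the adjusted model to the diffusion measures does not raise the required N. These are powers for one test at 0.05, before any multiplicity correction.

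**2. Which measures each step covers.**

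| Measure | Rank (Table 2, Appendix 2) | Spearman + FDR | Adjusted regression (11.4) |
|---|---|---|---|
| DTI: FA, RD, MD | primary | yes | not stated |
| NODDI: NDI | primary | yes | not stated |
| T1 volume | secondary | yes | yes |

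**3. Illustration for one pair.** Let age correlate a with the MRI measure and b with the subtest, with no other link. The raw correlation is then a·b and the correlation given age is 0. The protocol gives no values for a and b; 0.3 to 0.5 is an assumed range. Simulation at n = 81, two-sided 0.05, 4,000 replicates per setting:

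| a = b | Raw r = a·b | Spearman rejects | Age-adjusted coefficient rejects |
|---|---|---|---|
| 0.3 | 0.09 | 12% | 4.9% |
| 0.4 | 0.16 | 27% | 5.1% |
| 0.5 | 0.25 | 58% | 5.2% |

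Repeat runs moved the Spearman column by a point or so, up to 28% and 59% in the last two rows.

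**4. The same null under the planned FDR step.** The summary table in Appendix 2 lists 42 subtest–tract pairs and 51 subtest–region pairs. With FA, RD and MD per tract and NDI per region, the primary family is 42 × 3 + 51 = 177 tests. Section 11.4 states q = 0.05 only for Study 3, so it is assumed here. MRI measures and subtests are taken as independent given age.

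| a = b | Mean number declared significant | Share of 177 | Studies with at least one |
|---|---|---|---|
| 0.3 | 0.7 | 0.4% | 31–33% |
| 0.4 | 11 | 6% | 87% |
| 0.5 | 77 | 44% | about 100% |

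With age adjustment and the same FDR step, the mean is below 0.1 of 177. A differently assumed family of 390 tests (30 MRI measures × 13 subtests) gives shares of 0.3%, 5.5% and 44%, so the pattern does not hinge on the exact count.

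**The case against.** **Volumetric may be loose drafting.** Section 11.3 powers Study 2 on a regression coefficient for brain regions in general, so regression may have been meant for all MRI measures. On that reading the power statement fits the primary measures. This is possible but weak: the preceding sentence of 11.4 separates volume from density and connectivity, and intracranial volume among the covariates suits a model written for volumes.

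**The plan is provisional.** Section 11.4 says it will be finalised with a statistician and posted on the Open Science Framework, and Spearman is called exploratory. That is fair, and no passage makes Spearman the deciding test. But the text states which measures receive adjusted models, leaves out its own primary ones and gives them no other test. Provisional status does not cure a stated rule.

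**Single-test rates are not what the plan would produce.** This stands. A reader might take 12%, 27% and 58% as the expected false-positive rates. The planned FDR step cuts the per-pair share sharply at the lower two settings, and hardly at all as a safeguard against any false finding at the upper two.

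**Objective iii is not wholly unadjusted.** This also stands. The objective concerns measures of neurodegeneration, and section 4.2 lists volumetry first without ranking it. The adjusted volumetric regressions answer part of the objective.

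**Conclusion.** The point holds as a mismatch within the protocol. The measures ranked primary for Study 2 lack the covariate adjustment given to the secondary ones, and read literally the sample size in 11.3 describes only the secondary analysis.

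A reader might infer that the diffusion results are confounded by age. The protocol does not show that: it reports no correlation of age with any MRI measure or subtest. The supported statement is that they are open to confounding by age, sex and education, which 11.4 itself names as potential confounders. The consequence ranges from minor (0.4% of pairs after FDR, at assumed correlations of 0.3) to severe (44% at 0.5). These figures rest on n = 81, equal correlations for all measures, independence given age, and q = 0.05.

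**What to change.** In 11.4, replace the restriction to volumetric measures so that the adjusted regression is also fitted for the primary DTI measures (FA, RD, MD) and NODDI measure (NDI) in the tracts and regions listed in Appendix 2. Adjust for age, sex and education throughout, and for intracranial volume in the volume models only. Apply Benjamini-Hochberg to that family of adjusted coefficients, state q, and base the Study 2 primary conclusion on them. Keep the raw Spearman correlations as the exploratory step. The regression-based calculation in 11.3 then refers to the primary measures; it should also say whether the test is one- or two-sided, since 64 holds only for the former.

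Cost: a few degrees of freedom out of 81 and some extra analysis. Section 6.2 already collects the covariates. Table 5 schedules publication of the analysis plan by January 2026, so if it is already posted, a dated update is needed. Lesion load from the BIANCA step in the imaging pipeline could serve as a sensitivity covariate for the diffusion models, but that is optional.
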